6. PROTOCOL DEVIATIONS

Protocol deviations and violations will be recorded by the site separately from the clinical database. The CRO/Shire will classify the protocol deviations and violations per the agreed protocol violation and deviation management plan. The Shire study team will review the protocol deviations and their classification throughout the study and before database lock.

Decisions of the review will include:

- Accuracy of protocol deviations and violations categorization.
- For any criteria for protocol deviations that can be completely implemented by a computer program, the detailed algorithm will be agreed upon. Details of such algorithms will be included in the derived dataset specifications and finalized before database lock.

Confirmed protocol violations and protocol deviations will be documented in the Protocol Violation/Deviation tracker tool for the study. Protocol deviations/violations will be summarized by category and site for each treatment group of the antecedent studies, current treatment (SHP465) for each enrollment type, and overall for the Safety Set. Protocol deviations/violations will be listed for the Safety Set.

7. DEMOGRAPHIC AND OTHER BASELINE CHARACTERISTICS

7.1 Demographic and Other Baseline Characteristics

Descriptive summaries of demographic and baseline characteristics will be presented for the Safety Set and FAS by treatment group of the antecedent studies (SHP465 or Placebo), current treatment of SHP465 for each enrollment type (rolled over or direct enrollment), and current treatment of SHP465 for overall.

The following demographic characteristics will be summarized in the following order in the tables: age, age group (4-5 years, 6-12 years), sex, ethnicity, race, weight, height, and body mass index (BMI). In addition, other baseline characteristics such as years since diagnosis of ADHD, baseline ADHD-RS-5 Child, Home Version total score for children aged 4-5 years and for children aged 6-12 years, and baseline Clinical Global Impressions-Severity (CGI-S) will be summarized. Baseline is defined as the last assessment before the first administration of the investigational product for Group B and as the non-missing assessment for the last visit of the antecedent study for Group A.

Age, weight, height, BMI, years since diagnosis of ADHD, ADHD-RS-5 Child, Home Version total score for children aged 4-5 years and for children aged 6-12 years will be summarized as continuous variables using number of subjects, mean and SD, median, and minimum and maximum values. Sex, ethnicity, race, and baseline CGI-S will be summarized as categorical variables using number of subjects and percentages for each category. For Group A, all summarized values will be taken from the baseline value from antecedent studies, while for Group B, summarized values will be taken from the Screening Visit (Visit 1), except for baseline ADHD-RS-5 Child, Home version Total Score and baseline CGI-S, which will be taken from the Baseline Visit (Visit 2). In addition, baseline weight and baseline height will be summarized in both conventional and international system of units.

Age will be calculated as the difference between date of birth (DOB) and earliest date of informed consent (DINFC) (i.e., consent date from antecedent studies for Group A and consent date from SHP465-308 for Group B), truncated to months, using the following:

- $\text{Age} = \text{floor}(\text{intck}(\text{'month'}, \text{DOB}, \text{DINFC}) - (\text{day}(\text{DINFC}) < \text{day}(\text{DOB}))) / 12$

BMI will be calculated using one of the following:

- $\text{Weight in pounds} * 703 / (\text{Height in inches})^2$
- $\text{Weight in kilograms} / (\text{Height in meters})^2$

Number of years since diagnosis of ADHD will be based on the date of the earliest informed consent (i.e., consent date from antecedent studies for Group A and consent date from SHP465-308 for Group B). Demographics and baseline characteristics will be listed for the Safety Set.

7.2 Medical History

Medical history will be collected at the Screening visit from antecedent studies for subjects in Group A and at the Screening Visit (Visit 1) for subjects in Group B. Medical history will be listed for the Safety Set.

The psychiatric diagnosis will be established using the Mini-International Neuropsychiatric Interview for Children and Adolescents (MINI-KID) Version 7.0.2 for DSM-5 Disorder at the Screening visit (Visit 1) for subjects in Group B only and will be listed for the Safety Set.

ADHD non-medication treatment history, behavioral therapy history, collected at the Screening Visit of antecedent studies for subjects in Group A and at the Screening Visit (Visit 1) for subjects in Group B, will be listed for the Safety Set.

For ADHD medication history collected at Screening Visits, version WHODRUG March 2017 of the World Health Organization (WHO) drug dictionary will be used to classify ADHD medications by preferred term. ADHD medication history will be summarized separately by the number and percentage of subjects receiving each medication within each preferred term by treatment group of the antecedent studies, current treatment (SHP465) for each enrollment type, and overall for the Safety Set. ADHD medication history will be listed for the Safety Set.

8. EXTENT OF EXPOSURE AND TREATMENT COMPLIANCE

8.1 Exposure to Investigational Product

Exposure to the investigational product (SHP465) will be summarized for the Safety Set by treatment group of the antecedent studies, current treatment (SHP465) for each enrollment type, and overall. The following statistics will be calculated by visit for the investigational product:

- Days of dosing: number of days on which dose information was available and non-zero
- Total dose (mg) for SHP465: total number of capsules taken \times dose level
- Average daily dose (mg/day) for SHP465: the total dose / total days of dosing
- Cumulative dose (mg) for SHP465: sum of total dose since start of treatment

The following statistics will be calculated for the investigational product for the whole treatment period:

- Total days of dosing = sum of the number of days dosed for each visit during that period
- Duration of exposure in weeks = the total number of days dosed / 7 days per week
- Total dose (mg) for SHP465 = total number of capsules taken \times dose level
- Average daily dose (mg/day) for SHP465 = the total dose / total number of days of dosed

An appropriate statistical summary will be applied to each of the above statistical quantities.

Subjects will be categorized in 4 week increments by overall duration of exposure in days and will be presented by subject counts and percentages.

In addition, person-time (overall total exposure in days) will be derived for SHP465. It is calculated as the total number of days in which SHP465 was taken for each subject (total days of dosing for the Treatment period), and then sum over all subjects for the Treatment period.

All dosing information, for example, total dose, average daily dose and cumulative dose, will be listed.

If a bottle has missing start and end dates then the subject's dose information from this bottle will be treated as missing. In particular, for the subjects who are lost in the follow up after the Baseline Visit (Visit 2), it will not be assumed that any of the investigational product has been ingested unless there is a post-baseline safety assessment. The days, from which there are no records showing that subjects have taken investigational product, will be excluded from the calculation of exposure. Subjects that do not return the investigational product but return to the site for the following visit will have the dose return information entered into the database on the scheduled visit.

8.2 Measurement of Treatment Compliance

Investigational product dosing compliance during the whole treatment period, are defined as the total number of capsules actually taken by a subject during that period divided by the total number of capsules expected to be taken during the same period multiplied by 100. The total number of

capsules actually taken is calculated by the total number of capsules dispensed minus the number of capsules returned. If a bottle is not returned, the number of capsules returned for that bottle will be imputed to zero, unless it is the last visit during study. If a subject is early terminated from the study without returning any bottles or providing number of capsules returned on any bottles that are dispensed at the visit before early termination, the number of capsules taken from these bottles will be treated as missing. The number of capsules expected to be taken is calculated as the number of days the subject was in the particular period multiplied by the number of capsules to be taken per day during that period.

Summary statistics for investigational product compliance will be presented by treatment group of the antecedent studies, current treatment (SHP465), and overall for and the whole treatment period for the Safety Set. The investigational product treatment compliance will be categorized as <80%, 80-120%, or >120% for and the whole treatment period. The category 80-120% is considered compliant for analysis purpose. The categorical data will be presented for the Safety Set.

Calculated compliance data for each subject will be listed.

9. PRIOR AND CONCOMITANT MEDICATION

Version WHODRUG March 2017 of the WHO drug dictionary will be used to classify prior and concomitant medications by preferred term.

Prior medication is defined as any medication taken prior to the date of first dose of investigational product in this study.

Concomitant medication is defined as any medication with a start date prior to the date of the first dose of investigational product and continuing after the first dose of investigational product or with a start date between the dates of the first dose and last dose of investigational product, inclusive.

Any medication with a start date after the date of the last dose of investigational product (post-treatment) will not be considered a concomitant medication

Both prior and concomitant medication usage will be summarized separately by the number and percentage of subjects receiving each medication within each preferred term by treatment group of the antecedent studies, current treatment (SHP465) for each enrollment type, and overall for the Safety Set. Medications can be counted both as prior and concomitant medication. Multiple medication usage by a subject in the same category will be counted only once for the purpose of the summaries.

All prior, concomitant and post-treatment medications will be listed for the Safety Set.

10. EFFICACY ANALYSES

All efficacy analyses will be performed using the FAS. Efficacy data will be summarized descriptively and no formal statistical tests will be performed. Only post-baseline assessments from Visit 3 (Week 1) up to Visit 16 (Month 12) that were collected on or 2 days after the last dose of investigational product will be analyzed. Summarization will be by treatment group of the antecedent studies, current treatment (SHP465) for each enrollment type, and overall.

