10.2 Key Secondary Efficacy Endpoint(s) and Analysis

10.2.1 ADHD-RS-5 Child, Home Version

To assess long-term efficacy, ADHD-RS-5 Child, Home version will be administered to children aged 4-5 years and 6-12 years. Baseline ADHD-RS-5 total score is defined as the last valid assessment prior to taking the first dose of investigational product for Group B and as the baseline value from the antecedent study for Group A. The observed and change from baseline in ADHD-RS-5 total score will be summarized at each applicable visit using the number of subjects, mean, SD, median, minimum, maximum values, and 95% confidence interval. A corresponding line graph of mean change from baseline and associated 95% CI in ADHD-RS-5 total score by visit and treatment group of the antecedent studies and current treatment (SHP465) for each enrollment type will be presented.

The items in the ADHD-RS-5 will also be grouped into 2 subscales: hyperactivity/ impulsivity (9 items for hyperactivity/impulsivity) and inattentiveness (9 items for inattentiveness). Each subscale will be summarized descriptively at each applicable visit. A corresponding line graph of mean change from baseline and associated 95% CI in the ADHD-RS-5 subscale scores by visit and treatment group of the antecedent studies and current treatment (SHP465) for each enrollment type will be presented.

Summaries will be repeated by age group (4-5 years and 6-12 years), sex, race (white and non-white), and ethnicity sub-group.

ADHD-RS-5 scores, including individual, subscale, and total scores, will be listed for FAS.

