11. SAFETY ANALYSES

Safety data will be analyzed for the Safety Set by treatment group of the antecedent studies, current treatment (SHP465) for each enrollment type, and overall. Safety endpoints include the occurrence of TEAEs, vital signs (systolic and diastolic blood pressure, and pulse), height, weight, body mass index (BMI); clinical laboratory and ECG results, C-SSRS, and sleep questionnaires (PSQ and CSHQ). For each safety endpoint, the last value collected before the first dose of investigational product in this study will be used as baseline for all analyses of that safety endpoint. Except for adverse event data, only post-baseline assessments from Visit 2 (Week 0) up to Visit 16 (Month 12) that were collected on or 2 days after the last dose of investigational product will be analyzed. A Final on-Treatment Assessment (FoTA) will be defined as the last valid assessment obtained after Baseline and whilst on investigational product (on or before 2 days after the last dose date).

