11.3 Vital Signs (Including Height and Weight)

The averaged values of the 3 measurements collected for blood pressure and pulse at each visit will be used for all summaries and determination of PCIs. Summaries for vital signs will be presented by treatment group of the antecedent studies, current treatment (SHP465) for each enrollment type, and overall.

Descriptive statistics for vital signs (sitting systolic and diastolic blood pressure, pulse and weight) and their changes from baseline at each post-baseline visit and FoTA will be presented in a summary table. These summaries will also include BMI. BMI will be automatically

calculated using the height and weight collected at each visit. In the case of multiple assessments at post-baseline visits, the first readable value at the visit will be used in the summary tables.

Additionally, figures with the mean change from baseline \pm SD of the vital signs values (sitting systolic and diastolic blood pressure, and pulse) will be presented by visit for each treatment group of the antecedent studies and current treatment (SHP465) for each enrollment type.

Height, weight and BMI will also be converted to percentile values based on the subject's age and sex at each visit and summarized categorically (<5th, 5th to <95th, and \geq 95th) at each visit and at the FoTA. Post-baseline shifts in height, weight and BMI percentile category (<5th, 5th to <95th, and \geq 95th) from baseline will be summarized at each visit and at the FoTA. In addition, z-scores for weight and BMI will be based on the subject's age at each visit and will be summarized categorically (<-2, \geq -2 to <-1, \geq -1 to <1, \geq 1 to <2, and \geq 2) at each visit and at the FoTA. Percentiles and z-scores will be derived using the CDC growth charts ([Kuczmarski et al. 2002](#)). A SAS program for the 2000 CDC Growth Charts will be used to derive the percentiles and z-scores (www.cdc.gov/nccdphp/dnpao/growthcharts/resources/sas.htm).

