18.4 Repeated or Unscheduled Assessments of Safety Parameters

If a subject has repeated assessments before the start of investigational product, then the results from the final assessment made prior to the start of investigational product will be used as baseline.

If a subject has repeated assessments at any post-baseline visit, the first recorded assessment will be assigned to the visit for generating descriptive statistics. For vital signs (sitting systolic and diastolic blood pressure, and pulse), this will be the average of the 3 measurements from the first recorded assessment.

If final on-treatment safety assessments are repeated or unscheduled, the last post-baseline assessment will be used as the final on-treatment assessment for generating descriptive statistics. For vital signs (sitting systolic and diastolic blood pressure, and pulse), this will be the average of the 3 measurements from the last post-baseline assessment.

However, all post-baseline assessments will be used for PCI value determination and all assessments will be presented in the data listings.

All repeat and unscheduled visits will be listed.

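### SAP 10 and 11 omit the word *before* from the last-dose window, so the data-inclusion rule as written contradicts the by-visit summaries it governs

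*SAP*

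**What the plan says.** SAP section 10 sets the rule for every efficacy summary. It admits only post-baseline assessments from Visit 3 to Visit 16 "that were collected on or 2 days after the last dose of investigational product will be analyzed". SAP section 11 sets the matching rule for safety. It exempts adverse event data and admits only post-baseline assessments "from Visit 2 (Week 0) up to Visit 16 (Month 12) that were collected on or 2 days after the last dose".

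The next sentence of section 11 defines the FoTA as the last valid value after baseline and on drug, with the window "on or before 2 days after the last dose date". That version contains *before*; the two inclusion rules do not.

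The rest of the SAP plans analyses that need values from throughout treatment:

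- Section 10.2.1: "The observed and change from baseline in ADHD-RS-5 total score will be summarized at each applicable visit". Section 10.2.2 does the same for CGI-I.
- Section 11.3, for vital signs: "their changes from baseline at each post-baseline visit and FoTA will be presented in a summary table".
- Sections 11.4 (ECG), 11.5.2 (PSQ) and 11.5.3 (CSHQ) also summarize by visit.
- Section 18.4: "However, all post-baseline assessments will be used for PCI value determination".

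Protocol section 9.8 commits to ADHD-RS-5 summaries at every on-therapy visit, and SAP section 17 declares no change from the protocol.

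**The concern.** Both sentences are exclusion rules, because each opens its condition with *only*. Without *before*, the condition describes a short span that starts on the last-dose date, not everything up to a cut-off. Coded as written, it would remove the on-treatment visits that the by-visit tables and line graphs are meant to show.

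The two possible readings also do different jobs. An upper limit keeps all on-treatment values and drops those taken more than 2 days after stopping drug. The literal text keeps only values at the very end of dosing. The cut-off matters here: SAP section 1 records that the sponsor terminated the study early, and protocol section 4.3 asks for an early termination visit whenever drug is stopped. Some final assessments may therefore fall close to the limit.

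Section 11 has a second inconsistency. Its post-baseline range starts at Visit 2 (Week 0), whereas section 10 starts at Visit 3. Section 11 itself defines safety baseline as the last value before the first dose in this study, and the protocol starts dosing on the morning after Visit 2.

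**Working it through.** The plan gives no figure to reproduce. The study is descriptive (SAP 2.6) and the sample size has no statistical basis (SAP 2.5). The check is a count of scheduled visits kept under each reading.

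**Inputs**

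- Post-baseline visits: Visits 3 to 16, on days 7 and 14 and then every 30 days from 30 to 360 (SAP 2.4, protocol Tables 1 and 2). Count: 2 + 12 = 14.
- Visit windows: ±2 days for Visits 3 and 4, ±5 days for Visits 5 to 16 (same tables).
- L is the date of the final dose. SAP 9, 11.1 and 18.5 use last dose in that sense, so reading it as the most recent daily dose before each visit does not fit.

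**Step 1: can two scheduled visits fall within L to L+2?** The smallest gap between consecutive visits is the earliest date of the later one minus the latest date of the earlier one.

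- Visit 3 to 4: (14 − 2) − (7 + 2) = 12 − 9 = 3 days.
- Visit 4 to 5: (30 − 5) − (14 + 2) = 25 − 16 = 9 days.
- Later pairs: 30 − 5 − 5 = 20 days.

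The smallest gap, 3 days, exceeds the 2-day span. At most one scheduled visit per subject can qualify.

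**Step 2: loss under the literal reading.** For n scheduled visits, at most 1 is kept and at least (n − 1)/n is lost. This applies to measures taken at every visit.

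| Last seen at | n | Kept at most | Lost at least |
|---|---|---|---|
| Week 2 | 2 | 1 | 1/2 = 50.0% |
| Month 1 | 3 | 1 | 2/3 = 66.7% |
| Month 6 | 8 | 1 | 7/8 = 87.5% |
| Month 12 | 14 | 1 | 13/14 = 92.9% |

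**Step 3: the readings compared**, for a completer with all visits on their nominal days (final visit on day 360).

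| Last dose (day) | Literal, L to L+2 | Narrower, L or L+2 only | Upper limit, up to L+2 |
|---|---|---|---|
| 360 | 1 of 14 | 1 of 14 | 14 of 14 |
| 359 | 1 of 14 | 0 of 14 | 14 of 14 |
| 358 | 1 of 14 | 1 of 14 | 14 of 14 |
| 357 | 0 of 14 | 0 of 14 | 13 of 14 |

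The third column arises because the text does not say whether the day after the last dose counts. Under the upper limit, the only visit lost is one taken more than 2 days after the last dose.

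**Step 4: Visit 2.** Protocol 6.2.3, 7.1.1.3 and 7.1.1.4 start dosing the morning after Visit 2. SAP 11 takes the last pre-dose value as baseline. A scheduled Visit 2 value is therefore pre-dose and cannot be post-baseline. Post-dose values before Visit 3 can still exist, because protocol 7.1 and 7.1.2 allow unscheduled visits.

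**The case against.** The strongest reply is that nobody would program the literal text. Naming a visit range that runs up to Visit 16 has little purpose if only one end-of-dosing record counts. The very next sentence of section 11 has the window right, and the by-visit summaries show the intent. This stands: the intended rule is evident. It does not make the printed rule correct, because an analyst still has to override an explicit exclusion with wording borrowed from another definition.

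A reader might infer more than the documents support:

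- *The plan discards almost all efficacy and safety data.* That requires the literal reading, which the surrounding text rules out. Adverse events are exempt and have their own 3-day rule (SAP 11.1). PCI determination uses all post-baseline values (SAP 18.4), and FoTA has its own correctly worded window.
- *The rule empties every table.* Laboratory summaries run only from baseline to Visit 16/ET (SAP 11.2), a record that even the literal rule would mostly keep. Subjects stop at different times, and SAP 18.3 assigns early termination visits to the next nominal visit, except for laboratory data. By-visit rows would be sparse, not all empty before Visit 16.
- *Only 1/14, about 7%, of planned assessments survives.* That fraction is for a 12-month completer and measures taken at every visit. With early termination, many subjects may have fewer visits.
- *Baseline values enter the PCI counts through Visit 2.* The word post-baseline in the same sentence already keeps pre-dose Visit 2 values out. The label is inconsistent, but that harm does not follow.

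**Conclusion.** The concern holds as a drafting error in an operative data-inclusion rule, and it should be corrected. As printed, sections 10 and 11 contradict the by-visit summaries, the PCI rule and the FoTA window. On the literal reading at most one scheduled visit per subject is kept: at most 1 of 14 for a 12-month completer and 1 of 8 for a subject last seen at Month 6. With the intended upper limit, a completer whose last dose is within 2 days before the final visit keeps 14 of 14.

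These counts assume that visits fall within their windows, that last dose means the final dose, and that the measure is taken at every visit. The size describes what the sentence would do if coded as written; it is not an expected loss of data. The Visit 2 start is a smaller inconsistency in the same sentence, with no demonstrated effect on the counts.

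**What to change.** In SAP sections 10 and 11, replace the window with: *collected on or before 2 days after the date of the last dose of investigational product*. This brings both rules into line with the FoTA definition.

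In section 11, also replace the phrase that starts the post-baseline range at Visit 2 (Week 0) with: *assessments collected after the first dose of investigational product in this study*. Pre-dose Visit 2 values are then plainly baseline, and unscheduled safety assessments between the first dose and Visit 3 stay in. Simply changing Visit 2 to Visit 3 is not advisable, because it could exclude those first-week values and create a new conflict with section 18.4.

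The cost is two edited sentences, with no new data, analyses or tables. Any program already written should be checked against the corrected window.
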